# **Transcranial Photobiomodulation for reducing autism symptoms in children.**

*May 1, 2022*

PROTOCOL TITLE:

Transcranial photobiomodulation for reducing autism symptoms in children.

PRINCIPAL INVESTIGATOR:

Name	[name]
Department	N/A
[contact]

RESEARCHERS:

Name	[name]
Department	N/A
[contact]

Name	[name], CFA, Esq.
Department	N/A
[contact]

Name	[name]
Department	N/A
[contact]

1.0 Purpose of the study:

The purpose of this 10-week feasibility study is to assess the tolerability, safety and efficacy of Transcranial LED Therapy for language learning and reducing symptoms of autism in children.

The investigators propose to enroll up to 30 participants, 2-7 years old, all of whom have recently completed the IRB approved study by JelikaLIt. They all have been previously diagnosed with moderate to severe ASD by licensed professionals according to the Diagnostic and Statistical Manual of Mental Disorders, Fifth Edition (DSM-5) criteria for Autism Spectrum Disorder (ASD).

This will be an one-arm, open label study. Participants who were in the placebo condition in the previous study, will receive the treatment. Participants who were in the active condition in the previous study will repeat the course of treatment after the intermission of 3-6 months (depending on when they completed the study).

The hypothesis to be tested is that exposure to photobiomodulation will reduce children's symptoms of autism, as measured by the reduction of the Mean Scores of the Childhood Autism Rating Scales, compared to the initial baseline.

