**7.6 On-going Data Collection:** Parents will be asked to keep a daily diary of the child's behavior, specifically – words spoken, comprehension of instructions, eye contact, his sleep pattern, number of tantrums, anxiety, social interaction and eating. Qualitative data will be collected through short weekly interviews with the parents. These interviews can take place either in [name] office during the child's treatment or by phone. During those weekly interviews, the parents will be asked questions about their children's responsiveness to language, number of words they can produce, eye-contact, anxiety, frequency of tantrums, eating, and difficulties falling asleep and sleeping through the night. Please see attached proposed script for the weekly call. The qualitative data will be used to further inform and supplement quantitative data.

The study will collect qualitative and quantitative data. The quantitative data will be the total CARS2 scores of the participants, obtained before and after the study is done. Repeated-measure t-tests will be used to analyze quantitative data. In addition, we will collect Before and After Prefrontal cortex EEG from the control and experimental treatment groups to measure electrophysiological changes in Prefrontal cortex. after treatment. EEG data will be analyzed (using Time-Frequency analysis), and after baseline normalization, the data will be used in aggregate to compare conditions numerically. In addition, we will obtain qualitative data from weekly parental interviews, during which we will ask participants' parents about their children's behavior (see attached protocol). Qualitative data will be used for information purposes and will supplement quantitative data.

The PI will analyze quantitative and qualitative data. An independent contractor (a neuroscientist) will be analyzing the collected EEG data at the end of the study, however, the individuals conducting the analysis will not have access to the private identifiable information.

**7.8 Confidentiality:** Participants' confidentiality will be protected by assigning them Study ID. The quantitative data will be analyzed and reported only as aggregate (averages and F scores). The qualitative data will be studied only by the researchers and, if reported for illustrative purposes only, it will be attached to the Study ID (not the identifying information). The participants will be asked for consent to report qualitative data with the Study ID.

●

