### 13.0 Risks to Participants:

Potential Risks	Mitigating Factors
Some questions may be very personal or upsetting to the parents	Parents may skip any questions that they do not want to answer.
The child may feel uncomfortable wearing the headband and may want to take it off early	
If the child wants to take off the headband, we will first encourage him to wear it, by attempting to divert his attention to other things, such as toys and music.
 
If, however, the child insists on taking off the headband, he / she will not be forced to wear it and he / she may be able to take it off before the conclusion of the session.

Breach of confidentiality (child's data being seen by someone who shouldn't have access to it)	We'll keep all children identifying information separate from the research data, but we'll be able to link it by using a study ID. We will destroy this link after we finish collecting and analyzing the data.
The child maybe receiving concomitant medical treatment	Even though there are no interaction of the tPBM with any medications, children currently receiving any psychotropic medications on a regular basis, will be excluded from participating in this pilot-study. This will be determined during initial screening.
The child might be receiving behavioral Intervention such as ABA simultaneously with participating in the study.	
There is no known negative interaction of this treatment with any behavioral treatment.
 
The children should be able to receive their regular behavioral therapies while being enrolled in this study.
 
Clinicians will monitor (based on parental and therapists' interviews) each child's progress.

There may be risks that we do not know about yet. Exposure to LED lights is not known to have any negative side effects.	
After years of study, there are no known negative side effects of photobiomodulation.
 
Throughout the study, we'll tell parents if we learn anything that might affect their decision to let their child participate.
 
Minor transient side effects may include headaches, agitation, and hyper-activity. These side effects are sometimes observed in the beginning of the treatment and usually resolve on their own. Parents will be informed of these potential minor side-effects in the Consent form.

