#### 15.0 Data Monitoring Plan to Ensure the Safety of Participants:

We will conduct weekly interviews with the parents, asking them questions about child's behavior and functioning to collect both safety and efficacy data. The interviews will be conducted either by telephone or in person (per parental choice). Please attached interview protocol. [name], a licensed clinical psychologist will review the data. The detailed qualitative data will be collected. No statistical analysis is necessary.

If a participant shows sudden developmental regress, we will recommend immediate neurological evaluation and his/her participation will be discontinued (unless this participant has been manifesting regress prior the start of the study). If two participants suddenly manifest signs of regress (not anticipated, not seen before in prior photobiomodulation studies), we will immediately discontinue the study.

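### Both mandatory safety triggers in protocol section 15.0 act only on developmental regress; the visible text requires no action for other serious new events and plans no count of side effects

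*Protocol*

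**What the plan says.** Protocol section 1.0 states that the purpose "is to assess the tolerability, safety and efficacy of Transcranial LED Therapy". Section 15.0 gathers safety information through the weekly parent interview, which a licensed clinical psychologist reviews. It then sets two mandatory rules. A child with sudden developmental regress is referred for neurological evaluation and discontinued, unless the regress pre-dates the study. At study level, "If two participants suddenly manifest signs of regress (not anticipated, not seen before in prior photobiomodulation studies), we will immediately discontinue the study". On analysis of these data it says "No statistical analysis is necessary".

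Section 13.0 lists the expected side effects: "Minor transient side effects may include headaches, agitation, and hyper-activity". It adds: "These side effects are sometimes observed in the beginning of the treatment and usually resolve on their own". Section 9.0 (rationale for the device) adds tiredness and links tiredness and headache to first-time users. Exclusion criteria 1 to 4 in section 4.0 bar entry for severe self-injury or aggression, another psychiatric or neurological disorder, an unstable medical condition, or a significant skin condition at the procedure site.

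Section 7.6 defines the numerical outcome: "The quantitative data will be the total CARS2 scores of the participants, obtained before and after the study is done". EEG is analysed separately. The interview topics listed there start with responsiveness to language and continue "number of words they can produce, eye-contact, anxiety, frequency of tantrums, eating, and difficulties falling asleep and sleeping through the night", with a pointer to a document outside the text: "Please see attached proposed script for the weekly call".

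**The concern.** The plan treats four kinds of condition as serious enough to keep a child out, but does not say what happens if one of them begins during treatment. A first seizure, for example, would require no step under the visible rules unless it came with developmental regress. The entry criteria are not predictions of device effects; the point is only that no action is named.

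The second part concerns what the study can report. Tolerability and safety come first among its purposes, but the visible text plans numbers only for CARS2 and EEG. If side effects are neither asked about in a fixed way nor counted, the study could finish without a stated rate, or a bound on one, for any of them. The children are 2 to 7 years old, and section 10.0 describes their comprehension and responsiveness as limited, so a headache may go unreported unless a parent is asked about it directly. Up to 14 children who had sham in the earlier study would be first-time users here, the group to which section 9.0 ties headache and tiredness.

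**Working it through.** The documents give no event rate or operating characteristic for the safety rule, so there is no figure of the plan's own to reproduce. The check is a reading of the visible rules, followed by arithmetic on what counting would give and what the fix would cost.

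**1. Rules side by side (protocol)**

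| Provision | Section | What sets it off | Required action for a non-regress event? |
|---|---|---|---|
| Child-level trigger | 15.0 | Sudden regress, one child | No |
| Study-level trigger | 15.0 | Sudden regress, two children | No |
| Device not forced on the child | 10.0, 13.0 | Discomfort or refusal | No; tolerance of the device only |
| Withdrawal by the family | 8.0 | Family's choice | No |
| Withdrawal by the study | 13.0 | Session not rescheduled within 7 days | No; attendance only |
| Restart offer | 13.0 | Week missed through sickness, under 8 weeks done | No; attendance only |
| Clinicians follow progress | 13.0, behavioural-therapy row | None stated | No |
| New information given to parents | 13.0 | Something learned | No; information only |

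Both mandatory triggers (2 of 2) concern regress. The visible SAP text deals only with CARS and contains no safety rule.

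**2. Side effects against listed topics**

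Sections 13.0 and 9.0 name four: headache, agitation, hyper-activity and tiredness. In the section 7.6 interview list, agitation has a partial proxy (tantrums, anxiety) and so does tiredness (sleep). Headache and hyper-activity have none, there or in the diary list. This describes the prose list, not the script.

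**3. What a count would give**

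With zero events in n children, the exact one-sided 95% upper limit is 1 − 0.05^(1/n).

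- n = 30 (maximum enrolment, section 5.0): 1 − 0.05^(1/30) = 9.5%.
- n = 14 (former sham children, section 2.4, if all return): 1 − 0.05^(1/14) = 19.3%.

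**4. How often the proposed study-level review would occur**

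No rate is given, so take an assumed range: 30 children, four serious event types, independent, each with the same per-child probability p. Let T = P(X ≥ 2) with X ~ Bin(30, p). The chance of at least one same-type review is 1 − (1 − T)^4, and the expected number of children held is 30 × [1 − (1 − p)^4].

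| p per type | T | Chance of a review | Expected children held |
|---|---|---|---|
| 0.5% | 0.0099 | 3.9% | 0.6 |
| 1% | 0.0361 | 13.7% | 1.2 |
| 2% | 0.1205 | 40.2% | 2.3 |

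**5. Why the minor side effects should stay outside the mandatory rule**

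Suppose the four named side effects were also triggers, making eight types. Let agitation and hyper-activity each occur at an assumed rate q and the other six types at 1%. The chance of a review is 1 − (1 − T_q)^2 × (1 − 0.0361)^6.

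- q = 5%: T_q = 0.446, giving 75%.
- q = 10%: T_q = 0.816, giving 97%.
- q = 20%: T_q = 0.989, giving over 99%.

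A review would then be close to routine, driven by behaviour that is common in autism.

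**The case against.** The strongest reply is that the safety plan incorporates an interview script that is not in the text. The topics in section 7.6 largely mirror the hoped-for benefits in section 12.0, so their silence on headache is weak evidence about the safety questions actually asked. That stands: the interview part is a request to check the script. Section 6.0 is also absent from the text available and could hold a relevant rule.

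The statement that no statistical analysis is needed could be read as meaning that events will go unrecorded or unreported. The documents do not support that. Interview data are kept by study ID and could be tabulated afterwards. What can be said is that no tabulation is planned in the visible text.

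A reader might also infer that children are left unprotected or that serious harm is likely. The documents do not support that either. Caregivers attend every session, treatment is given in the office twice a week, parents keep a daily diary, a psychologist reviews the interviews, families may leave at any time, and section 13.0 says that the consent form tells parents of the side effects. The device has an FDA Non-Significant Risk designation, and the protocol describes its side effects as minor and temporary. These safeguards lower the severity, but none of them sets a required action or a count for an event other than regress.

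Finally, the zero-event limits hold for any samples of 30 and 14. They show what counting would allow the study to state; they do not measure the gap.

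**Conclusion.** The point holds for the visible text. Section 15.0 requires action only for sudden regress, no other visible rule covers the four serious event types, and no count of side effects is planned for a study whose first-named purposes are tolerability and safety. This is more than missing detail: following the stated rules would require nothing after such an event and would yield no event count.

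Severity is low to moderate, in view of the risk designation and the informal safeguards. The conclusion rests on the text available and would narrow if the script or section 6.0 already contains the items or rules. The 19.3% limit assumes that all 14 former sham children enrol; with fewer it is wider. The review and hold frequencies rest on assumed rates, equal and independent across event types, and are illustrations only.

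**What to change.** Use the existing weekly interview and the psychologist already assigned to review it.

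1. Unless the script already does so, ask each week about headache, agitation, hyper-activity and tiredness relative to the child's own baseline, with one open question on any new medical event. Report the number of children with each, with an exact confidence limit, overall and for first-time users.
2. Hold treatment and recommend medical evaluation for a new seizure or neurological diagnosis, an unstable medical condition, a significant skin problem at the device site, or severe self-injury or aggression that is new or worse than the child's own baseline. The hold lasts until the reviewer clears the child and does not count against the 7-day rescheduling window in section 13.0. Naming these events directly is better than citing exclusion 2, whose psychiatric wording sits awkwardly with inclusion 7.
3. A second child with the same type of serious held event prompts a study-level review, not an automatic stop.

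Leave persistent minor side effects to the reviewer's judgement, without a mandatory hold or study-level trigger, and leave the regress rule as written.

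The cost is one protocol paragraph, up to five interview items and one summary table, with no new committee, visit or staff. The downside is a few treatment pauses, some caused by background behaviour, and a longer interval between CARS2 pre-test and post-test for a held child. Under the assumed rates of 0.5% to 2% per type, the chance of at least one study-level review is about 4% to 40%.

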#### 16.0 Data, and if applicable, Specimen Banking:

The raw research data will be stored for 6 years. The identifying parental information will be kept for a year, for potential follow up interviews. The consent form will include their permission to keep identifying data for a year.

Although we do not plan to re-contact the participants after the study is complete, a follow up interview in 6 months or a year could be useful to assess the sustainability of the benefits of photobiomodulation. In this case, we will be applying for a separate IRB (minimal risks) to conduct the follow up interview. Presently, we do not plan to do it (although we recognize that it could potentially be useful for research purposes).

The data will be stored in encrypted, password protected files in a secure cloud.

#### 17.0 Data Sharing:

Only aggregated data will be shared with scientific community (via publications). Only aggregated data will be shared with potential investors. If individual data (e.g., from an interview) is shared for illustrative purposes, identifying information will NOT be shared (STUDY ID will be assigned to each participant).

# Data Collection and Statistical Analysis

## Primary Analyses

The last author, a licensed psychologist experienced in the use of CARS in clinical practice, conducted blinded Before and After CARS ratings for all participants. The final CARS evaluations were performed immediately after the final treatment session. CARS scores were analyzed using the independent sample t-test. We compared the differences from the baseline between both groups, calculating both the average difference and 95% CI within each group and between groups.

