**7.0 Procedures Involved:**

7.1 Location: The study will use pre-test and post-test design. The entire study on the children will be done in the office. The weekly interview with the parent may be done either in office or by phone, as preferred by the parent.

7.2 Conditions: There will be only one active condition.

7.3 Participants: The participants will be 2 to 7 years old children previously diagnosed with moderate or severe ASD. Children of all genders and races will be included in this study.

7.4 Treatment: The treatment will take place twice a week for up to 30 minutes at a time.

During the study, while participants will be wearing the photobiomodulation device, they may be playing with their parent or the experimenter, using the toys of their choice (out of the many available in the experimenter's office). The caregivers will be present during the experiment at all times. When the child and the parent arrive, they will be welcomed to the office, and introduced to the toys.

The child will be encouraged to play with toys and interact with the parent (or the experimenter).

If the child becomes uncomfortable, the parents will be able to leave the experiment without any punishment. No coercion or deception is involved in this study.

7.5 Pre and Post-Testing:

The following measurements will be used for pretest and post-test.

- Childhood Autism Rating Scale (CARS2)

CARS 2 scores will be compared for analyses.

In addition, EEG will be collected from the participants pre and post -treatment in each session. Mobile FDA cleared EEG device from Brain Scientific will be used to collect children's pre and post test EEG.

There is no known danger of EEG collecting. In this study it will be using for measuring the efficacy treatment only.

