#### 14.0 Provisions to Protect the Privacy and Confidentiality of Participants and the Research Data:

Participants will be only interacting with [name], [name], Esq, or [name] (researcher). Participants and their parents will be tested individually, in a quiet room, and their confidentiality will be protected, as they won't be interacting with each other or with anybody else outside of the researchers.

The participants will be explained that they can refuse to answer any question. They can also refuse to participate in the study at any time. We do not anticipate uncomfortable questions, however, we will assure the participants that their level of comfort is of utmost importance, and we will explain to them that there is no penalty involved for their refusal to answer any specific question.

Only [name] and [name] will be able to access individual information. The participants will be immediately assigned Study ID number and only STUDY ID will be used for data analysis and reporting. Only aggregated data will be used for further reporting to the scientific community or to the business community. Individual data will be reported for illustrative purposes only with STUDY ID (not identifying personal information).

The following information will be included as data: Signed consent form (immediately scanned and stored in a cloud). Pre and Post-test Cars2 scores (with STUDY ID assigned). Weekly interview data (with STUDY ID assigned).

Identifying information will include Name and Age, Gender and number of therapy hours of the participant, Name and phone number of the parent. Children's age, gender and number of therapy hours will be used for matching purposes (for assigning to the control or treatment condition). Neither names of the participants nor names and phone numbers of their parents will be used for data analysis or reporting. Their names and phone numbers will be stored separately, in encrypted (password protected) file, in a secure cloud. Secure clouds as well as encryption and password protection will be used to protect identifying information.

The raw research data will be stored for 6 years. The identifying parental information will be kept for a year, for potential follow up interviews. The consent form will include their permission to keep identifying data for a year.

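### The SAP's blinded, two-group CARS assessment fits the earlier sham-controlled trial and cannot apply to this one-arm study, whose supplied protocol text gives no rater safeguards for its only tested clinical endpoint

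*SAP*

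**What the plan says.** **Design.** Protocol section 1.0: "This will be an one-arm, open label study". Section 7.2: "There will be only one active condition". Up to 30 children who took part in the earlier trial may enrol (section 5.0).

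**Endpoint and test.** Protocol section 7.6 takes total CARS2 before and after the study as the quantitative data and names repeated-measures t-tests. EEG is to be compared numerically, with no test named. Section 7.5 lists CARS2 as the pre- and post-test measure and does not say who scores it.

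**Rating procedure.** The only description is under Primary Analyses in the SAP, which gives the task to one of the report's authors: "a licensed psychologist experienced in the use of CARS in clinical practice, conducted blinded Before and After CARS ratings for all participants". On timing it adds: "The final CARS evaluations were performed immediately after the final treatment session". On the test it says: "CARS scores were analyzed using the independent sample t-test".

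**Roles around the rating.** Protocol section 14.0 limits contact with families to a closed group of researchers. Under section 15.0, which covers the weekly parent interviews, "a licensed clinical psychologist will review the data". Section 7.6 adds: "The PI will analyze quantitative and qualitative data".

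**The concern.** CARS is scored by clinician judgement, so a rater who expects improvement can move the score. A sham arm with a rater blind to allocation spreads much of that expectation over both groups, and the between-group difference is protected. A one-arm before-after comparison has no such protection: any shift in how the rater scores the second visit goes straight into the mean change.

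The SAP's wording suggests that this has been dealt with, but it describes a safeguard that the present design cannot provide. Without that wording, the supplied text says nothing about how the CARS2 rating is protected. At stake is whether a significant fall in CARS2, the stated hypothesis of the study, could come from the rating alone, and whether a reader of the SAP would wrongly take the endpoint to be blinded.

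**Working it through.** **1. Which trial does the SAP text describe?**

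| Feature | SAP | Earlier trial (protocol 2.4) | This study (protocol 1.0, 5.0, 7.2, 7.6) |
|---|---|---|---|
| Groups | Active 16, Sham 14 | 16 active, 14 sham | one, active |
| CARS test | independent-sample t | F statistic given | repeated-measures t |
| Tense | past, with results | completed | planned |
| Blinding to allocation | claimed | possible | impossible |

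The SAP matches the earlier trial in group sizes and design, and matches this study in neither. The protocol also keeps some two-group remnants (control and experimental conditions in 4.0 and 7.6, placebo in 10.0, matching in 14.0), but sections 1.0 and 7.2 are explicit that there is one arm.

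**2. What protects the rating in this study?** In the supplied text, no section names the CARS2 rater, masks the rater to visit order, keeps the rater out of treatment sessions, bars access to interview or diary data, or withholds the pre-test form. A final rating made straight after the last session, if carried over from the SAP, would also make the time point hard to hide.

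**3. The SAP's own figure** (Outcomes, Primary Outcome). Active change = 43.5 − 33.7 = 9.8. Sham change = 40.6 − 38.0 = 2.6. Difference = 7.20, against 7.23 stated, which agrees given the rounded means. The interval 2.357 to 12.107 has midpoint 7.232 and half-width (12.107 − 2.357)/2 = 4.875.

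- SE = 4.875 / t(0.975, 28) = 4.875 / 2.048 = 2.380
- t = 7.23 / 2.380 = 3.04, two-sided p = 0.005, consistent with the stated 0.01 at two decimals
- Pooled SD of change = 2.380 / √(1/16 + 1/14) = 6.50

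**4. Illustration for this study.** Assumptions: N = 30 (the stated maximum), SD of change 6.5, two-sided 5% (the protocol states no level), true change zero.

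- SE = 6.50 / √30 = 1.187
- Smallest significant mean fall = t(0.975, 29) × SE = 2.045 × 1.187 = 2.43 points
- For a uniform rater shift δ, P(p<0.05) = P(|T| > critical t), where T is noncentral t on N − 1 df with noncentrality δ/SE

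| Assumed shift | N=30, SD 6.5 | N=20, SD 6.5 | N=30, SD 5 | N=30, SD 8 |
|---|---|---|---|---|
| 1 point | 12.9% | 10.0% | 18.5% | 10.2% |
| 2 points | 37.0% | 25.7% | 56.3% | 26.3% |
| 3 points | 68.5% | 49.9% | 88.8% | 51.0% |

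The nominal rate is 5%. At N = 30 the smallest significant fall is 1.87 points for SD 5 and 2.99 for SD 8. The shifts, N = 20 and SDs 5 and 8 are assumed; no document gives a size for rater bias.

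**The case against.** The strongest reply is that the blinding sentence is correct where it belongs. In the 16 v 14 trial a rater could be blind to allocation, and the protocol for this study never calls CARS2 blinded. It declares an open-label feasibility study, in which expectancy is inherent. That stands. A reader might infer that this study's ratings were, or would be, falsely reported as blinded. The documents do not show that: a two-group sham analysis could not be carried out here, and the root fault is that the SAP does not fit the protocol.

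Three other tempting readings also go too far:

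- **That the rater treats the children, hears the parents or sees earlier scores.** The rater is not named. The psychologist who reviews interviews in section 15.0 is not identified as the CARS2 rater, and the PI's analysing data is not the same as rating children. Overlap is possible, not shown.
- **That no safeguard exists at all.** Parts of both documents are not in the supplied text. The claim is limited to what is there.
- **That a 2-point shift on top of the sham fall of 2.6 gives 4.6 and so passes the SAP's 4.5-point threshold.** In the SAP that figure is a per-child responder cut-off, not a criterion for a mean. The 2.6 may also include regression to the mean, maturation, concurrent therapy and the expectations of a rater who did not know the allocation.

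The reply does not remove the gap. If the SAP text governs, its blinding claim cannot hold here; if it does not, the supplied text specifies no rater. Replacing only the t-test would leave the rating unprotected.

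**Conclusion.** The point holds in this form. The blinded, two-group CARS assessment in the SAP matches the earlier trial and cannot apply to this one. The supplied protocol text leaves rater expectancy uncontrolled on the only clinical endpoint with a named test; the SAP's responder analysis is CARS as well.

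The size is illustrative. At N = 30 and SD 6.5, a mean fall of about 2.4 points is enough for significance, and an assumed rater shift of 1 to 3 points raises the false-positive rate from 5% to between about 13% and 69%. This rests on carrying the pooled SD over from the earlier trial, full enrolment, a two-sided 5% test, no true change and a uniform shift. It shows how sensitive the test is to rater drift and does not estimate the bias in this study. The point should be addressed, with medium confidence, because who rates CARS2 is not stated.

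**What to change.** 1. **SAP.** State that the blinded wording and the two-group analysis belong to the earlier trial. For this study, describe CARS2 as an open-label clinician rating analysed by the protocol's paired t-test. Deleting the one word would not be enough, since the design mismatch would remain.
2. **Pre-test form.** Lock it once completed, so that the rater has no access to item or total scores when rating the post-test.
3. **Rater.** State in the protocol who rates CARS2. Where existing staffing allows, choose someone who does not deliver sessions and does not see interview or diary data before the post-test is locked. Leave the licensed psychologist's safety review in section 15.0 unchanged. If the roles cannot be separated, report the overlap as a limitation.

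The cost is protocol and SAP wording, some loss of scheduling flexibility and a less favourable description of the endpoint. No arm or visit is added. The documents do not show whether a second qualified rater is available, so step 3 is conditional. The rater would still know that every child is treated, and probably which visit is the last, so these steps reduce expectancy bias without removing it.
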